15.0 DATA COLLECTION, STUDY MONITORING, AND DATA DISCLOSURE

15.1 Data Collection and Reporting

An eCRF will be completed for each subject who receives at least one dose of study drug. All entries on the eCRF must be supported by original source documentation (e.g., laboratory reports, medical records) maintained at the investigational site.

The Investigator will make all safety assessments (AEs and vital signs) on an ongoing basis. The Investigator is required to review all entries on the eCRF and sign at appropriate time intervals.

15.2 Study Monitoring

All aspects of the study will be monitored carefully by the Sponsor's designees with respect to current Good Clinical Practice (GCP) and Standard Operating Procedures (SOP) for compliance with applicable government regulations. It is the responsibility of the Investigator to provide all study records, including eCRFs, source documents, etc., for review and source document verification by the clinical monitor.

All eCRFs will be 100% source verified against corresponding source documentation (e.g., office and clinical laboratory records) for each subject. Clinical monitors will evaluate periodically the progress of the study, including the verification of appropriate consent form procedures, review of drug accountability and preparation procedures, adherence to dosing procedures, and the verification of the accuracy and completeness of eCRFs. Clinical monitors will also ensure that all protocol requirements, applicable FDA regulations, other requirements, and Investigator's obligations are being fulfilled.

15.3 Audit and Inspection

The Sponsor or representative may conduct audits at the trial site(s). Audits will include, but are not limited, to protocol compliance, drug supply, presence of required documents, the informed consent process, and comparison of eCRFs with source documents. The Investigator agrees to participate with audits conducted at a reasonable time in a reasonable manner.

Regulatory authorities worldwide may inspect the trial site during or after the trial. The Investigator should contact the Sponsor immediately if this occurs and must fully cooperate with the inspections conducted at a reasonable time in a reasonable manner.

15.4 Deviation from Clinical Trial Protocol

Deviations from the protocol are to be avoided. If a deviation occurs, the Investigator must promptly report the deviation to the study monitor.

The Investigator (or designee) will record any failure to follow the protocol because of any other medical unavoidable reason to avoid the subject's urgent risk and record a document as soon as possible stating this and the reason. It must be submitted to the Sponsor and the director of the study site.

15.5 Retention of Records

The Investigator must retain all study records required by ARS and by the applicable regulations in a secure and safe facility. The Investigator must notify ARS of any change in the location, disposition, or custody of the study files. The Investigator/Institution must take measures to prevent accidental or premature destruction of essential documents, that is, documents that permit evaluation of the conduct of a study and the quality of the data produced, including paper

copies of study records (e.g., subject charts) as well as any original source documents that are electronic as required by applicable regulatory requirements.

All study records must be retained until whichever is the later day in the following: (1) At least the date of approval for the drug or (2) the date when 3 years have passed since the discontinuation or completion of the study. No records relating to this study should be disposed of without the written approval of ARS. It is the responsibility of ARS to inform the Investigator/Institution as to when these documents no longer need to be retained.

15.6 Data Disclosure and Subject Confidentiality

Subject medical information and video recordings obtained as a result of this study is considered confidential and used only for study evaluation purposes. Disclosure to third parties other than those noted below is prohibited. All reports and communications relating to subjects in this study will identify each subject only by number. Medical information resulting from a subject's participation in this study may be given to the subject's personal physician or to the appropriate medical personnel responsible for the subject's welfare. Data generated as a result of this study are to be available for inspection on request by FDA or other government regulatory agency auditors, the Sponsor clinical monitor (or designee), and the IRB/EC.

All laboratory specimens, evaluation forms, reports, and other records that leave the site will be identified by a coded number to maintain subject confidentiality. All records will be kept in a locked and secured area. All computer entry and networking programs will be identifiable only by coded numbers. Clinical information will not be released without written permission from the subject, except as necessary for monitoring by the IRB, the FDA, or the study Sponsor.

Any information, inventions, or discoveries (whether patentable or not), innovations, suggestions, ideas, and reports, made or developed by the Investigator(s) as a result of conducting this study shall be promptly disclosed to the Sponsor and shall be the sole property of the Sponsor. The Investigator agrees, upon the Sponsor's request and at the Sponsor's expense, to execute such documents and to take such other actions, as the Sponsor deems necessary or appropriate, to obtain patents in the Sponsor's name covering any of the foregoing.

The results of this study will be published under the direction of the Sponsor. Results will not be published without prior review and approval by the Sponsor and Study Investigator.

16.0 PROTECTION OF HUMAN SUBJECTS

16.1 Basic Principles

The study will be conducted in accordance with the relevant regulatory requirements, this protocol, and ethical principles that are consistent with the GCP guideline developed by the International Conference on Harmonization of Technical Requirements for Registration of Pharmaceuticals for Human Use (ICH). This clinical trial will also be conducted in compliance

with Declaration of Helsinki, protocol, Standard specified in the relevant local regulations. Prior to initiation of the study, the Investigator and the Sponsor should obtain approval from the IRB/IEC on this protocol and any further amendments, and the subject information and informed consent form.

Any suspected serious breaches must be immediately reported to the Sponsor. A serious breach is a breach of the conditions and principles of GCP in connection with the study or the protocol, which is likely to affect, to a significant degree, the safety of the subjects or the scientific value of the study.

Personnel involved in the study will be qualified by education, training, and experience to perform their respective tasks.

16.2 Institutional Review Board/Ethics Committee

The Investigator or designee agrees to provide the IRB/EC with all appropriate material, including a copy of the ICF. The study will not be initiated until the Investigator obtains written approval of the research plan and the ICF from the appropriate IRB/EC and copies of these documents are received by the Sponsor. Appropriate reports on the progress of this study will be made by the Investigator to the IRB/EC and Sponsor in accordance with applicable government regulations and in agreement with the policies established by the Sponsor. The Sponsor ensures that the IRB/EC complies with the requirements set forth in 21 CFR Part 56 (Code of Federal Regulations).

16.3 Informed Consent

The Investigator is responsible for:

- Explain the subject of the study, the risks and benefits expected from participating in the study, and that the participation is voluntary so that the subject can understand.
- Obtain informed consent to participate in the trial from the subject by signing or signing the consent form and entering the date before starting the study procedure and study drugs.
- Properly answer questions from subjects at any time during the trial and if new information that can affect the subject's intention to continue the trial is obtained while the subject is participating in the trial, the information is promptly communicated to the subject.
- Give a copy of the written consent form to the study participants and keep one copy at the study site.

16.4 Subject Health Injury and Insurance

In general, if a subject is health-injured as a direct result of the investigational products, the Sponsor or its contracted insurance company will pay for reasonable and necessary medical

treatment for the health-injury. If laws or regulations of the locality in which the study is taking place require additional payment of expenses, the Sponsor should comply with such laws or regulations. Where applicable, the Sponsor will arrange for specific insurance coverage. If health damage occurred to a subject participating in the clinical trial due to the willful or gross negligence of Investigator's site, indemnification will be discussed based on the contract with the site. The indemnification for the health damage and the payment to subjects will be described in the ICF.

16.5 Completion of the Study

If the clinical trial is completed at the study site, the Investigator will notify the director of the study site that the trial has been completed and provide an approximate summary in writing. The director of the study site will promptly notify the IRB/EC and the Sponsor in writing about the completion.

Appendix A: Schedule of Study Procedures

Table 1: Schedule of Study Procedures

| Study Procedure Study Day | Screening Day -90 to -1 | Treatment Period 1 | | Treatment Period 2 | | Treatment Period 3 | |
|--|----------------------------|-----------------------|-----------|-----------------------|-----------|-----------------------|-----------|
| | | pre-dose | post-dose | pre-dose | post-dose | pre-dose | post-dose |
| Signed informed consent | X | | | | | | |
| Inclusion/Exclusion Criteria | X | X | | | | | |
| Admission to Clinical Site | | X | | X | | X | |
| Medical history | X | X | | | | | |
| Complete or targeted physical exam | X | X | | X | | X | |
| Vital signs ^a | X | X | X | X | X | X | X |
| Height and Weight | X | | | | | | |
| Hematology, Serum Chemistry, Coagulation, and Urinalysis | X | | | | | | |
| HIV Antibody and Hepatitis Tests | X | | | | | | |
| Urine Drug and Cotinine, Saliva/Urine Alcohol Screen | X | | | | | | |
| Prior and Concomitant medication assessment | X | X | X | X | X | X | X |
| Urine pregnancy test ^b | X | | | | | | |
| Adverse event assessment ^c | | | X | X | X | X | X |
| ECG (12-Lead in triplicate) ^d | X | | | | | | |
| Study Medication | | | X | | X | | X |
| Patient reported pruritus/hive score and VAS for pain ^e | | X | X | X | X | X | X |
| Investigator-rated extent of urticaria and erythema score ^f | | X | X | X | X | X | X |
| | | | | | | | |
| | | | | | | | |
| | | | | | | | |
| Discharge assessment ^d | | | X | | X | | X |
| | | | | | | | |

- Vital signs (BP, PR, temperature, and respiratory rate) will be taken at pre-dose, and at 5 (\pm 2 min), 20 (\pm 2 min), 30 (\pm 2 min), 60 (\pm 5 min), and 120 (\pm 5 min) minutes after dosing. Actual times by hour/minutes/seconds will be recorded.
- A urine pregnancy test will be administered to females of childbearing potential at screening.
- AE assessment will begin after dosing and continue until discharge. AEs will also be solicited at the follow up telephone call.
- ECG is to be performed in triplicate.
- Patient reported pruritus/hive score and VAS pain assessments will be done pre-dose, and at 5 (\pm 2 min), 10 (\pm 2 min), 15 (\pm 3 min), 30 (\pm 5 min), 45 (\pm 5 min), 60 (\pm 10 min), 120 (\pm 10 min) minutes and every 60 minutes (\pm 10 min) after dosing until the discharge criteria (the time when symptoms of acute urticaria have been effectively treated based on the Investigator's or his/her designee's opinion will be recorded, not necessarily when subjects discharge) is met for acute flare and until urticaria symptoms return to baseline for chronic spontaneous urticaria. The actual time of the assessment and of when the symptoms return to baseline will be recorded.
- Investigator-rated extent of urticaria and erythema will be done pre-dose, and at 5 (\pm 2 min), 10 (\pm 2 min), 15 (\pm 3 min), 30 (\pm 5 min), 45 (\pm 5 min), 60 (\pm 10 min), 120 (\pm 10 min) minutes, and every 60 minutes (\pm 10 min) after dosing until the discharge criteria (the time when symptoms of acute urticaria have been effectively treated based on the Investigator's or his/her designee's opinion will be recorded, not necessarily when subjects discharge) is met for acute flare and until urticaria symptoms return to baseline for chronic spontaneous urticaria. The actual time of the assessment and of when the symptoms return to baseline will be recorded..

[figure not shown]

g.
i.

[REDACTED]

Discharge assessment will be done by Investigator or his/her designee once symptoms of urticaria have been effectively treated for an acute flare or returned to baseline for chronic spontaneous urticaria. Actual time by hour and minutes will be recorded. If the rescue medicine was required, it will be recorded.

[REDACTED]

Appendix B: Instructions for Use

| INSTRUCTIONS FOR USE neffy Epinephrine Nasal Spray (Single-Use) Use Only In Nose | | |
|---|--|--|
| 
neffy Nasal Spray device is for the emergency treatment of allergic reactions including anaphylaxis.
 
Read this Instructions for Use on how to use neffy.
 
Ask a healthcare provider if you have any questions on how to use neffy.
 
As you may require more than 1 dose, carry 2 neffy Nasal Spray devices with you whenever possible.
 
Your neffy Nasal Spray device:
  
Important Information:
 
 • Use only in the nose. Avoid spraying in the eyes or mouth. • Do not test or prime (pre-spray); each neffy can only be sprayed 1 time. • Each neffy Nasal Spray device contains only 1 dose and is for single-use only. Do not reuse. • Check your neffy periodically to be sure the expiration date has not passed. Replace your neffy before the expiration date has passed. • Contact a medical professional after using neffy to determine if more medical care is needed. | 
Dosing neffy Nasal Spray device
 
1A  Remove neffy from packaging (see Figure 1A). Pull open the packaging to remove the neffy Nasal Spray device.
 
1B  Hold device as shown (see Figure 1B). Hold the device with your thumb on the bottom of the plunger and a finger on either side of the nozzle. 
 • Do not pull or push on the plunger. • Do not test or pre-spray; each device has only 1 spray. 
 
1C  Insert tip of sprayer into a nostril until your fingers touch your nose (see Figure 1C). Keep the nozzle straight into the nose pointed toward your forehead. Do not angle the sprayer to the septum wall or outer wall of the nose.
 
1D  Press plunger up firmly until it snaps up and sprays into the nostril (see Figure 1D). If any error is made in dosing or any liquid drips out of the nose, repeat dosing with a second neffy Nasal Spray device.
 
⚠ Do not angle sprayer Do not angle the sprayer to the septum wall or outer wall of the nose.
 

 
+ Contact a medical professional after use Contact a medical professional to determine if more care is needed. Tell them that a neffy Nasal Spray has been used.
 | 
⌚ After 10 minutes, repeat dosing, if necessary Monitor patient for symptoms. If symptoms get worse or reoccur after 10 minutes, or if any error in dosing, use a new neffy Nasal Spray device to give a 2nd dose in the other nostril.
 
Disposing of used neffy Nasal Spray device:
 
 • Dispose of used neffy Nasal Spray device in household trash. • Do not recycle.  
Store neffy Nasal Spray in the blister pack provided.
 
 • Store below 77°F (25°C). Excursions permitted up to 122°F (50°C). • Allow to thaw for 20 minutes if inadvertently frozen. • neffy Nasal Spray freezes at temperatures below 5°F (-15°C). If this happens, the device will not spray. If neffy Nasal Spray is inadvertently frozen and is needed in an emergency, do NOT wait for neffy Nasal Spray to thaw. Get emergency medical help right away. However, neffy Nasal Spray may still be used if accidentally frozen by thawing it at room temperature for 20 minutes. 
Additional Information: Call [contact]
 
ARS Pharmaceuticals, Inc. [name]
 |

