3.2 Study Drugs

3.2.1 Test Product

ARS-1 is a solution formulation of epinephrine intended for nasal administration.

ARS-1 will be administered by IN administration using the commercial sprayer device at a dose of 1 mg and 2 mg epinephrine per spray delivered in a volume of 100 μ L aqueous solution.

Placebo is saline to be administered by IN administration using the commercial sprayer device delivered in a volume of 100 μ L aqueous solution.

Dosing will be conducted according to the Instructions for Use (IFU) ([Appendix B](#)).

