10.3 Drug Administration

After baseline safety assessments, subjects will be randomized to receive the following treatments at each of the three Treatment Periods:

- 1 mg per 100 μ L dose of ARS-1,
- 2 mg per 100 μ L dose of ARS-1, or
- placebo (100 μ L)

ARS-1 or placebo will be dosed to the nostril by the medical professional in a clinical setting per IFU ([Appendix B](#)). [REDACTED]

[REDACTED] Subjects will be monitored for both safety and symptom relief. Safety assessments will be performed after dosing and will include AEs and vital signs. Concomitant medications will be recorded.

Subjects should remain in the clinic as below:

- Acute flare: at least 2 hours after dosing and can discharge when the discharge criteria is met (the time when symptoms of acute urticaria have been effectively treated based on the investigator's or his/her designee's opinion will be recorded, not necessarily when subjects discharged). If no relief of pruritus symptoms after 2 hours, other acute interventions may be administered as rescue.

- Chronic spontaneous urticaria: until the urticaria symptoms returns to the baseline. [REDACTED]

The calendar date and 24-hour clock time of all doses will be recorded on the eCRF.

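### Sections 3.2.1 and 10.3 tie dosing to an unadapted emergency leaflet that allows a second spray for worsening or recurring symptoms, which conflicts in the readable text with the single-dose design

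*Combined protocol and SAP*

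**What the plan says.** Section 3.2.1 states: "Dosing will be conducted according to the Instructions for Use (IFU", pointing to Appendix B. Section 10.3 adds that ARS-1 or placebo "will be dosed to the nostril by the medical professional in a clinical setting per IFU". Neither readable passage says which parts of the leaflet apply.

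Appendix B is a general product leaflet. It opens by saying that the "Nasal Spray device is for the emergency treatment of allergic reactions including anaphylaxis". It contains two repeat instructions:

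- **Symptoms.** Under "After 10 minutes, repeat dosing, if necessary" it says "If symptoms get worse or reoccur after 10 minutes, or if any error in dosing, use a new" branded "Nasal Spray device to give a 2nd dose in the other nostril".
- **Drip or error.** In the dosing steps it says "If any error is made in dosing or any liquid drips out of the nose, repeat dosing with a second" device.

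The protocol itself is titled and described as single-dose (Section 3.1). Appendix A shows one study-medication entry per treatment period. Section 3.1.1 sets the nostril side by randomization. Section 3.1 asks that rescue be avoided for 15 minutes where possible. For an acute flare without relief of itch after 2 hours, it allows other acute treatments; it does not mention another study spray. Duration of effect belongs to a primary objective (Section 2.1) and ends when the grade is back at baseline (Section 14.3.1). Subjects with chronic spontaneous urticaria stay in the clinic until that return.

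**The concern.** The protocol adopts by reference a document that tells the user to re-treat on worsening or recurrence, while the trial intends to give one spray and watch what follows. The leaflet's 10-minute point falls inside the 15-minute period in which rescue should be avoided and well before the 2-hour rescue point. No readable sentence says which text prevails, and up to four centers could read it differently.

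If the symptom instruction were followed, three things would be affected:

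- Later scores in that period would describe two sprays, not the assigned one.
- The trigger is itself an outcome, so repeats need not be balanced across treatments. The comparison between doses that Section 14.3.1 allows, if both beat placebo, could be blurred.
- Safety is analysed by treatment received (Section 14.2), and a 4 mg period is none of the three planned treatments.

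**Working it through.** The plan gives no figure to reproduce. The check sets the texts side by side and counts what a repeat would touch.

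**1. Assessments after a repeat spray.** Inputs from Section 3.3 (efficacy, minutes): 5±2, 10±2, 15±3, 30±5, 45±5, 60±10, 120±10. Inputs from Section 9.3 (post-dose vital signs): 5±2, 20±2, 30±2, 60±5, 120±5. For a repeat at time t, the nominal count is the number of times > t. The low count uses (time − window) > t and the high count uses (time + window) > t.

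| Repeat at | Efficacy, of 7 (low–high) | Vital signs, of 5 (low–high) |
|---|---|---|
| 10 min | 5 (5–6) | 4 (4–4) |
| just after 15 min | 4 (4–5) | 4 (4–4) |
| just after 60 min | 1 (1–2) | 1 (1–2) |

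At t = 10 the five efficacy times are 15, 30, 45, 60 and 120. The sixth arises because the 10-minute score may be taken as late as 12 minutes. The first row is the largest case, since the symptom instruction starts at 10 minutes.

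**2. Total dose.** The leaflet names no strength, so assume that the same product is repeated. After a symptom-triggered repeat the total is d + d = 2d:

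- 1 mg period: 2 × 1 = 2 mg nominal, equal to the other active dose.
- 2 mg period: 2 × 2 = 4 mg nominal.

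After a drip or misfire, only a share f of the first spray is kept, and the total is d(1 + f). The documents give no f. Over the assumed range 0 to 1, a 1 mg period totals 1.0 to 2.0 mg and a 2 mg period 2.0 to 4.0 mg. At f = 0 the repeat simply delivers the assigned dose.

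**3. Duration of effect.** I take Section 14.3.1 to mean the time during which the grade is better than baseline. On the 0–3 itch scale, a flare that starts at 3 and clears to 0 can recur at 1 or 2 before it is back at baseline. One that starts at 2 and clears to 0 can recur at 1. At those levels symptoms have recurred in the leaflet's sense while the endpoint is still running, so a spray given then could change the recorded time of return.

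No effect on the treatment contrasts is estimated; the documents give no repeat frequency.

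**The case against.** The strongest reply is that no site would act this way. A medical professional doses in the clinic. The title, the design section and the one administration per period all say single dose. The leaflet addresses lay users, and its repeat step is headed as discretionary. Section 12.6 requires used sprayers to be accounted for, where the leaflet sends them to household trash, so the protocol seems meant to prevail. Read literally in a placebo period, the leaflet would even call for an active device, which suggests that only spray technique was intended. Section 12.4 (Administration of Study Drug) is listed in the contents but not readable, and text directly after the IFU reference in 10.3 is redacted. Either could hold the restriction.

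A repeat would also be traceable: "The calendar date and 24-hour clock time of all doses will be recorded on the eCRF", dispensing is logged and deviations are reported. Study drug is in restricted storage, so only recurrence in the clinic could prompt a repeat.

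Most of this stands. It makes re-dosing a possibility that rests on a literal reading, and it makes the fix conditional on the hidden text. It does not remove the conflict in the readable text: the technique-only reading is sensible but is not stated, and recording a second spray does not restore the single-dose observation.

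The drip or error instruction is a weaker case. Replacing a lost spray arguably completes the assigned dose, and forbidding it would exchange possible overdosing for possible underdosing. A reader might infer that every repeat in the leaflet contradicts the design; the documents do not support that for drips and misfires.

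**Conclusion.** The point holds as a conflict between the readable protocol and a leaflet that it adopts without limit. Severity is minor. If the symptom instruction were followed at 10 minutes, up to 5 of 7 fixed efficacy times (6 with visit windows) would follow two sprays. With the same product repeated, nominal totals would be 2 mg and 4 mg. A spray for partial recurrence could move the recorded return to baseline.

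A reader might go further and infer that the dose comparisons will be biased. The documents do not support this: the leaflet says only if necessary, the number of repeats and the direction of any bias are unknown, and the synopsis declares all analyses exploratory. A reader might also infer a demonstrated hazard at 4 mg. Section 3.2.2 cites safety up to 2 mg, but Section 1.2.4.1 reports exposure up to 4 mg with no serious adverse events. Nor can one conclude that the plan lacks a restriction, because Section 12.4 and part of 10.3 cannot be read.

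**What to change.** Unless Section 12.4 already says so, add to 3.2.1 and 10.3: *The IFU governs device handling only. No second study spray is given for worsening or recurring symptoms; these are treated under the protocol's rescue text.* Rescue stays as available as it is now.

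For a drip or misfire, the sponsor should choose one rule for all sites. One option is to replace only with the same assigned product, and only when the device visibly failed to discharge. Record any second spray, with product, nostril and time, as a deviation under Section 15.4.

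The cost is two sentences in two places, one misfire rule and minor eCRF recording; dose times and deviations are already captured. If replacement is allowed, sites need spare sprayers of each product. Section 3.1 calls the treatment period open-label, so replacing like with like breaks no blind. No patients or visits are added.
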